For the EMLA group , the specialist nurse who perform IV cannulation will determine the puncture site. A thick layer of EMLA cream (lidocaine and propiocaine 2.5%/2.5%) will be applied on a 1x1 cm² area of skin on the cannulation site. The transparent dressing will be covered on the cannulation site for 30 minutes, then remove it and clean the skin with a sterile cotton swab. Then nurse will perform IV cannulation for them.

For the distraction group , multiple distractions including toy whistles, cartoon books, TV showing cartoons, and various electronic products with video games will be provided for children to choose. They will be also taught breathing exercises (i.e. inhaling through the nose for 3 seconds and exhaling for 5 seconds, while they are counting) if they are willing. A play therapist play with the children for 5 minutes prior to and throughout the venipuncture procedure.

For the combined group , both EMLA cream and distraction techniques will be used. EMLA cream will be applied on the pre-puncture site for 30 minutes as the EMLA group, then the play therapist will encourage children to choose their favorite toys and play that with them 5 minutes before venipuncture or to do breathing exercises as the distraction group. During IV cannulation the play therapist will continue distracting the child with toys.

STATISTICAL ANALYSIS PLAN

Statistical Package for Social Sciences (SPSS Inc., Chicago, IL, USA) for Windows (version 22.0) with statistical significance set to $p < 0.05$.

To answer the question that is there significant statistical difference in venipuncture pain score among lidocaine group, Attention diversion group and Combination group, Mann Whitney and Kruskal-Wallis will be used to compare the 2 and 3 groups respectively. The results will be present in a table in the form of median and interquartile range if the data is non-abnormal distribution. Otherwise, use mean±standard deviation to describe the data.

To answer the question that is there significant statistical difference in children's salivary cortisol among lidocaine group, Attention diversion group and Combination group. Mann Whitney and Kruskal-Wallis will be used to compare the 2 and 3 groups respectively. The results will be present in a table in the form of median and interquartile range if the data is non-abnormal distribution. Otherwise, use mean±standard deviation to describe the data.

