To answer the question that is there significant statistical difference in children's HR, SpO₂ and venipuncture related findings like venipuncture times, venipuncture duration and indwelling needle duration of every child, Mann Whitney and Kruskal-Wallis will be used to compare the 2 and 3 groups respectively. The results will be present in a table in the form of median and interquartile range if the data is non-abnormal distribution. Otherwise, use mean±standard deviation to describe the data.

To answer the question that what's the preference for toys of children in Attention diversion group and Combination group, frequency distribution percentage will be used. To answer the question that is there significant statistical difference of children's choice in toys between Attention diversion group and Combination group, the chi-square test will be used. All the data will be present in a table in the form of median and interquartile range if the data is non-abnormal distribution. Otherwise, use mean±standard deviation to describe the data.

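### Does the 5-minute play step in the combined group spoil its comparison with EMLA cream alone?

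*Combined protocol and SAP*

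**What the plan says.** All the timings are in the Interventions section of the protocol.

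- **EMLA group.** The dressing stays on "for 30 minutes, then remove it and clean the skin with a sterile cotton swab. Then nurse will perform IV cannulation for them". No waiting time between cleaning and needle is given.
- **Combined group.** "EMLA cream will be applied on the pre-puncture site for 30 minutes as the EMLA group, then the play therapist will encourage children" to choose toys; the therapist is then to "play that with them 5 minutes before venipuncture", "or to do breathing exercises as the distraction group". Dressing removal and skin cleaning are not mentioned separately for this group.
- **Distraction group.** "A play therapist play with the children for 5 minutes prior to and throughout the venipuncture procedure". Breathing exercises are offered as well, described as "inhaling through the nose for 3 seconds and exhaling for 5 seconds, while they are counting", with no number of cycles.

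For pain scores and salivary cortisol the SAP states: "Mann Whitney and Kruskal-Wallis will be used to compare the 2 and 3 groups respectively". It does not single out combined versus EMLA. Its list of procedural outcomes covers "venipuncture related findings like venipuncture times, venipuncture duration and indwelling needle duration of every child". The Aim is to examine how well three interventions work, the third being cream and distraction together.

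**The concern.** Combined versus EMLA is the pair that many readers will take as showing what distraction adds to the cream. That reading needs the two groups to be alike in everything except distraction. On the page they are not: one has a play step after the cream step and the other does not. If the child is cannulated later after application in the combined group, time since application differs by group, and a Mann-Whitney test of the two groups cannot tell it apart from distraction.

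Two features add to the worry. The text does not say whether the dressing comes off before, during or after play, so cream contact might also differ. And the interval from application to needle is not among the timing variables that the SAP names, so the match between groups might not be checkable afterwards.

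**Working it through.** The plan states no figure for the interval, so there is nothing to reproduce. The check is arithmetic on the stated times, followed by a reading of the text.

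**Inputs from the Interventions section**
- Cream time: 30 minutes in both cream groups.
- Play before the needle: 5 minutes in the combined and distraction groups.

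**Inputs not given (assumed)**
- *c*: minutes for removal, cleaning and set-up, taken as equal in both cream groups.
- *s*: minutes for choosing toys.

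**Application-to-needle interval**

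EMLA group: 30 + *c*.

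| Reading of the combined group | Interval | Difference from EMLA | Cream contact |
|---|---|---|---|
| Dressing off and skin cleaned, then play | 30 + *c* + 5 | 5 min | 30 vs 30 |
| Play with the dressing on, then removal | 30 + 5 + *c* | 5 min | 35 vs 30 |
| Play starts at 30 min and overlaps removal and set-up | 30 + max(5, *c*) | max(0, 5 − *c*); 3 min if *c* = 2 | 30 vs 30 if the dressing comes off at 30 min |
| Play inside the 30 min | 30 + *c* | 0 | 30 vs 30 |

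In the first two rows *c* cancels. With *c* = 0, 5/30 = 16.7%; with *c* = 2, 5/32 = 15.6%. These percentages give scale only. If choosing toys takes extra time in sequence, the difference is 5 + *s*, so *s* = 1 to 3 gives 6 to 8 minutes. Five minutes is thus a nominal figure and not an upper limit.

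**Which reading fits the text**
- The cross-reference to the EMLA group most naturally carries over that group's whole cream step, including removal and cleaning at 30 minutes. Play with the dressing on would give 35 minutes of contact, against the stated 30.
- The word *then* puts play after the cream step, so play inside the 30 minutes also fits poorly.
- That leaves the first row, or the overlapping version of it: equal contact and a nominal gap of up to 5 minutes before any time for choosing toys. The order is inferred, because it is not written out.

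**Breathing exercises.** One cycle is 3 + 5 = 8 seconds, and no count is given. The distraction group is offered breathing on top of play, and the combined group's text ends with the therapist still using toys during cannulation. An average shift over the group would need an assumed split between play and breathing and an assumed breathing time, so none is given here.

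**Comparisons touched.** Three groups give three pairs. Combined versus distraction shares the 5-minute play step. EMLA versus distraction is cream against play and was never a test of adding one to the other. Only combined versus EMLA is open to the question.

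**Adjustment.** If the interval is set by group, it cannot be separated from group in any model. The SAP's silence on adjustment is therefore not a defect here.

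**The case for a change.** The strongest case for a change is this. A timing difference built into the groups is systematic: randomisation does not balance it and a larger sample does not remove it. Two members of staff could follow the text and deliver the combined group differently. A sentence on sequence and three recorded times would cost little and would let a reader check the match.

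Much of that is fair as description. The sequence is not spelled out, and a difference between the two cream groups could not be attributed to distraction alone. Recording the times would be harmless.

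It does not show that the plan goes wrong if followed. No objective in the documents is to isolate distraction, and the SAP asks only whether the groups differ. Play before the needle is part of the intervention, so the time it takes comes with it. The SAP's list of timing variables is illustrative, so an interval missing from it is not thereby known to go unrecorded. Whether a few minutes after a 30-minute application affects pain or cortisol needs information that the documents do not contain. The two descriptions differ without contradicting each other, so requiring equal intervals would set a clinical schedule rather than repair an inconsistency.

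**Conclusion.** No change to the plan is needed. The observation is correct: read in order, the combined group has a nominal 5-minute step between cream and needle that the EMLA group lacks. It is a consequence of delivering two interventions together, and the comparison of three strategies that the Aim describes remains sound.

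What remains is a matter of wording when results are reported: combined versus EMLA compares whole strategies. An analyst would say so without a new instruction, and spelling out the order of steps would add procedural detail without altering any planned test.

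This rests on two assumptions: that the cross-reference to the EMLA group carries over dressing removal at 30 minutes, and that handling time is similar in the two cream groups. If the dressing stayed on during play, contact would be 35 against 30 minutes; the contrast would still be one of strategies, with a further reason not to credit distraction alone. The conclusion would be different if the trial had stated an objective of estimating the separate effect of distraction added to the cream.

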Pharmacological and Non-pharmacological Interventions in Management of Peripheral Venipuncture related Pain: A Randomized Clinical Trial

NCT04275336

DATA: August 4,2020

STUDY PROTOCOL

Aim

This study aims to examine the effectiveness of three different interventions including EMLA cream, distraction techniques and the integrating of EMLA cream and distraction techniques in managing venipuncture pain and stress of children.

Design

A three-arm parallel, randomized controlled trial will be applied in this research. Eligible participants will be randomly assigned to into three groups: EMLA group, distraction group and combined group.

Interventions

Hard copies of informed consent will give to all parents, while children's assent and eligibility data will be obtained from face-to-face interviews. Eligible children will be randomly assigned to into three groups: EMLA group, distraction group and combined group. Nurses will explain the pain rating scales, pharmacological and non-pharmacological techniques, and the usage of intravenous cannulation. Every child will be accompanied by a parent throughout the whole process. At baseline, patients' age, sex and ethnicity will be recorded before they are grouped.

The nurse who will perform venipuncture for children had 10 years of venipuncture experience in the pediatric ward. The intravenous cannula used is 19 gauge x 0.7-in. needle and the whole procedure adhere to standard IV cannulation procedures. While cannulation is ongoing, an

observer monitor the children and complete the revised-FLACC scale (r-FLACC). The observer, a senior pediatric nurse from the surgical department who had received pain assessment training, watch the procedure through real-time surveillance video. The HR and SpO₂ of children will also be recorded.

Transparent waterproof adhesive skin dressing will use to fix the cannulation. The children and parents will give their own Wong Baker and r-FLACC ratings as soon as the procedure is over. The sample of saliva will be take using the cortisol saliva ELISA assay kit for quantitative determination of salivary cortisol levels to evaluate children's stress during venipuncture. Any adverse effects resulted from the IV cannulation or EMLA cream will be observed and recorded during their entire hospitalization.

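### The SAP does not name the scale or rater behind its venipuncture pain score, and does not say whether pairwise tests depend on the three-group test

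*Combined protocol and SAP*

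**What the plan says.** The pain paragraph of the Statistical Analysis Plan asks "is there significant statistical difference in venipuncture pain score among lidocaine group, Attention diversion group and Combination group". The score is in the singular, and no scale, rater or time point is attached to it. For the tests it says "Mann Whitney and Kruskal-Wallis will be used to compare the 2 and 3 groups respectively". The level appears once, in the opening sentence of that section ("for Windows (version 22.0) with statistical significance set to" p < 0.05).

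The Interventions section of the protocol describes several pain ratings:

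- During cannulation, an "observer monitor the children and complete the revised-FLACC scale (r-FLACC"). This person is "a senior pediatric nurse from the surgical department who had received pain assessment training".
- Afterwards, "The children and parents will give their own Wong Baker and r-FLACC ratings as soon as the procedure is over".

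If the child gives Wong-Baker and the parent r-FLACC, there are three ratings. The sentence does not say that, so four ratings (one of the two using both scales) or five (both using both) are also possible.

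On reporting, the pain paragraph says "The results will be present in a table in the form of median and interquartile range" for one kind of distribution and means with standard deviations otherwise. That fixes the table format, not which rating answers the question. The same pair of tests is planned for "salivary cortisol among lidocaine group, Attention diversion group and Combination group", and again for heart rate, SpO2 and the venipuncture measures. Nowhere is there a primary pain rating, a rule for when pair tests may be interpreted, or a multiplicity adjustment.

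**The concern.** Two separate gaps affect the same conclusion, and pain comes first in the stated Aim.

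**No named score.** A child, a parent and an observer can rate the same procedure differently. If they disagree about the arms, the plan does not say which of them decides. The choice could then be made with the results in view, and nobody could later show that it was not.

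**No gate.** Three arms give three pairs. The sentence on tests matches each test to a number of groups. It does not say whether a significant pair counts when the three-group test is not significant. If it does count, the error on even a single score exceeds the stated 5% when all arms are equal.

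**Working it through.** The documents give no sample size, power or overall error rate, so there is no figure of theirs to reproduce.

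**Inputs from the documents.** Level 0.05 (SAP, opening sentence); three arms (Design), hence 3 × 2 / 2 = 3 pairs; Mann-Whitney and Kruskal-Wallis tests (SAP); at least three pain ratings (Interventions).

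**Assumptions not in the documents.** Two-sided tests, equal arm sizes, large-sample behaviour and, for step 3 only, equal correlations between ratings of 0.5 to 0.9.

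**Step 1: one score, all arms equal, no gate.** At least one pair is significant when the largest standardised difference between two arms exceeds 1.96. This is the tail of the studentized range for three groups:

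P(range > 1.96 × √2) = P(range > 2.772), k = 3, infinite df = 0.1223, or **12.2%**.

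The formula for independent tests, 1 − 0.95³ = 14.3%, overstates it because the pairs share arms. Simulated rank tests at assumed sizes of 20, 40 and 100 per arm, on continuous and tied scores, gave 11.5% to 12.9%.

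**Step 2: the same with a gate.** A false pair claim now also requires a significant Kruskal-Wallis test, which happens 5% of the time when all arms are equal. The result is **5.0%**. If exactly one arm truly differs, only one null pair is left, so the error is no more than 5% with or without the gate.

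**Step 3: illustration of the unnamed score.** Suppose the gate is in place and a positive result on any one of three ratings is taken to show a pain difference. Large-sample simulation with all arms equal gives:

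| Assumed correlation | Any of three positive | All three must agree |
|---|---|---|
| 0.5 | 12.7% | 0.3% |
| 0.7 | 11.1% | 0.8% |
| 0.9 | about 8.5% | about 2.1% |

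If one rating is intended the error is 5.0%; if all must agree it is below 5%. Only the any-positive rule inflates it.

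**Step 4: an alternative to the gate for one named score.** Test each pair at 0.05/3. The critical value is z = 2.394, and P(range > 2.394 × √2 = 3.386) = 0.044, or **4.4%**.

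**Step 5: power cost of splitting alpha.** Take a three-group test with 80% power at 0.05: chi-square with 2 df, critical value 5.99, noncentrality 9.63. With that noncentrality fixed:

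| Level | Critical value | Power |
|---|---|---|
| 0.025 | 7.38 | 71% |
| 0.05/3 | 8.19 | 66% |
| 0.025/3 | 9.57 | 57% |

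**The case against.** The strongest reply is that these error rates belong to decision rules the SAP does not contain. Its pain question is about a difference among three groups, for which Kruskal-Wallis at 0.05 has a 5% error on one score. Reading pair tests only after a significant three-group test is common practice, and the SAP does not reject it. The singular wording fits one intended rating at least as well as several.

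Much of this stands. The 12.2% needs both the absence of a gate and equality of all three arms. A reader might infer that the plan as written carries an 8% to 13% false-positive rate for pain because several ratings are collected. The documents do not support that: they state no rule that any positive rating suffices and give no correlations. The number of ratings is itself uncertain.

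Two things do not fall away. An unstated gate cannot be checked by a reader or held to after the data are in. And if one rating is intended, the plan still does not say which. Planning to tabulate results does not answer that.

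**Conclusion.** The concern holds as an omission with a conditional numerical effect. The SAP names neither scale nor rater for its pain score while the protocol collects at least three ratings, and it states neither a gate nor an adjustment for the pair tests. On one score with all arms equal, the false-pair risk is 12.2% ungated and 5.0% gated, assuming two-sided tests and equal arm sizes. When exactly one arm differs, the missing gate costs nothing on a single score.

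The range of about 8% to 13% for accepting any of three gated ratings is illustrative only, and should not be read as the plan's error rate.

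This must be fixed before analysis. The reason is the missing deciding rating together with the missing gate: once results are known, a choice of rating can no longer be shown to be independent of them.

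**What to change.** Add to the SAP before the data are analysed:

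1. **Name the score.** Name one scale and one rater, chosen by the sponsor, as the primary pain score. Label the other pain ratings secondary.
2. **State the gate.** Interpret an outcome's pairwise Mann-Whitney tests only if its Kruskal-Wallis test is significant at the alpha assigned to that outcome, and test the pairs at that same alpha. With three arms this holds the error for that outcome at its assigned level. For one named score at 0.05, testing the three pairs at 0.05/3 each without a gate is a valid alternative. The same gate sentence can cover heart rate, SpO2 and the venipuncture measures.
3. **Assign the alpha.** Pain has 0.05 if cortisol is secondary. If the sponsor makes cortisol co-primary for stress, pain has 0.025 and cortisol 0.025. If several pain ratings are kept as primary, divide pain's alpha by their number and apply the gate at the divided level.

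This takes two or three sentences and no extra data. With one named score, the other pain ratings are no longer confirmatory. With the gate, no pairwise claim is made when the three-group test is not significant. Splitting alpha costs power: 80% at 0.05 becomes about 71% at 0.025, 66% at 0.05/3 and 57% at 0.025/3. Naming one score and keeping cortisol secondary avoids that loss.

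### Minor: the SAP's rule for choosing median/IQR or mean±SD is written the wrong way round in all four outcome paragraphs, and in the toy paragraph it does not fit a nominal variable

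*Combined protocol and SAP*

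**What the plan says.** The Statistical Analysis Plan has four outcome paragraphs: pain score; salivary cortisol; HR, SpO₂ and the venipuncture findings; and toy preference. The first three each contain the sentence "The results will be present in a table in the form of median and interquartile range if the data is non-abnormal distribution" and follow it with "Otherwise, use mean±standard deviation to describe the data". The fourth carries the same two-branch rule, but its subject is *All the data* instead of the results.

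In the first three paragraphs the inferential method stands just before the rule: "Mann Whitney and Kruskal-Wallis will be used to compare the 2 and 3 groups respectively". It does not depend on the distribution. In the toy paragraph the method for describing preference is "frequency distribution percentage will be used", and the comparison between the two distraction arms is by chi-square.

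**The concern.** The two branches of the rule are swapped. Data that are *non-abnormal* are normal data, and the plan gives them median and IQR. Everything else, including skewed data, falls to mean±SD. An analyst who followed the text would tabulate skewed outcomes by mean and SD, next to p-values from rank tests.

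The toy paragraph has a second problem, which correcting one word would not cure. Choice of toy is a nominal variable. Neither median/IQR nor mean±SD can summarise it, yet the closing sentence offers only those two forms, for *All the data*.

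The descriptive tables matter somewhat more than usual here because the SAP names no effect estimate. The group summaries are the only planned indication of how large any difference in the quantitative outcomes is.

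**Working it through.** The SAP gives no figure to reproduce on this point. The check is a reading of the four paragraphs, then a count of what the rule reaches.

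**Step 1. The rule, paragraph by paragraph**

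| SAP paragraph | Literal rule if normal | Literal rule otherwise | Other method named |
|---|---|---|---|
| Pain score | median/IQR | mean±SD | Mann-Whitney, Kruskal-Wallis |
| Salivary cortisol | median/IQR | mean±SD | Mann-Whitney, Kruskal-Wallis |
| HR, SpO₂, venipuncture findings | median/IQR | mean±SD | Mann-Whitney, Kruskal-Wallis |
| Toy preference (*All the data*) | median/IQR | mean±SD | frequencies and percentages, chi-square |

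The direction is the same in 4 of 4 paragraphs. Nothing elsewhere in the document states it the other way, so the SAP does not correct itself. Replacing *non-abnormal* with *non-normal* restores the usual convention in every place. That, and the near-identical wording, is why a single copied slip is the likeliest explanation.

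**Step 2. Does the rule drive any test?** No. The rank tests are named unconditionally in the three quantitative paragraphs, and chi-square in the fourth. Effect on tests and p-values: none.

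**Step 3. How many quantitative outcomes does it reach?**

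- Labels named: pain 1 + cortisol 1 + (HR, SpO₂, venipuncture times, venipuncture duration, indwelling needle duration) 5 = 7. The last three are introduced as "venipuncture related findings like venipuncture times, venipuncture duration and indwelling needle duration of every child", so the list is open.
- The pain label may stand for several ratings. In the protocol's Interventions section an observer completes the r-FLACC (1 rating). Then "The children and parents will give their own Wong Baker and r-FLACC ratings as soon as the procedure is over". If the child gives the Wong Baker and the parent the r-FLACC, that adds 2, for a total of 1 + 2 = 3. If both people give both scales, it adds 4, for a total of 1 + 4 = 5. A mixed reading gives 4.
- Variables if every rating counts: 7 − 1 + 3 = 9, up to 7 − 1 + 5 = 11.

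**Step 4. What does *All the data* cover?**

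- If it refers to the toy paragraph only, it covers 1 nominal variable, which it cannot describe.
- If it is a closing rule for the whole SAP, it still covers toy choice and also reaches the baseline variables in the Interventions section ("age, sex and ethnicity will be recorded before they are grouped"). The quantitative total becomes 9 + 1 = 10, up to 11 + 1 = 12, with age added. The nominal total becomes toy choice + sex + ethnicity = 3. Adverse effects are also recorded, but the form of that variable is not given, so they are left out of the count.

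On either reading the rule covers toy choice, where it does not fit.

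**The case against.** The best case on the other side is that this is close to copy-editing. The rank tests beside the rule make the intent fairly clear, no analysis depends on the rule, and the harm arises only if someone follows wording that was probably never meant. In the toy paragraph the specific instruction to use frequencies and percentages would govern in practice, so the table can be produced anyway. The baseline reading is conditional: the SAP promises no baseline table. The variable counts depend on how two sentences are read and do not measure a consequence. Finally, the usual rule would itself put mean±SD beside rank-test p-values whenever data look normal, and it needs a criterion for normality that the SAP does not give.

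Most of this stands as an argument about weight, and it is why the point is only minor. The counts show reach, not harm. The baseline reading is a possibility, not a finding. The remark about a missing normality criterion is right, and the fix should supply one. Mean±SD beside a rank test is less of a problem when data are near normal, because mean and median then nearly agree.

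The objection does not remove the error. A SAP settles reporting before results are seen. Here the written rule and the likely intended rule give opposite tables, so the analyst must either follow a reversed rule or depart from the plan.

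**Conclusion.** The concern holds, as a minor one. The descriptive rule is literally reversed in 4 of 4 outcome paragraphs. It affects how seven named quantitative outcome labels are tabulated (9 to 11 variables if the pain label covers every rating), and it is misapplied to at least one nominal variable, toy choice. Tests and p-values are unaffected.

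The reversal and the misfit in the toy paragraph are plain from the text. Two things are inference: that the cause is one copied slip for *non-normal*, and whether *All the data* is local to the toy paragraph or global. Neither changes the conclusion.

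**What to change.** - In the pain, cortisol and HR/SpO₂/venipuncture paragraphs, write: mean±SD if approximately normally distributed; otherwise median and interquartile range.
- Add one sentence on how normality will be judged, and whether within each arm or pooled.
- In the toy paragraph, state that toy choice is reported only as counts and percentages by group.
- If *All the data* was meant as a general closing rule, keep it with the corrected wording and restrict it to quantitative variables, including baseline age. Sex and ethnicity then fall outside it.

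The cost is SAP wording only: one corrected rule in three paragraphs, one clarified closing sentence in the fourth, and one added sentence on normality. Data collection and tests do not change.

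### Does the undefined toy choice, with breathing exercises worded differently in the two groups, undermine the planned chi-square test?

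*Combined protocol and SAP*

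**What the plan says.** The final paragraph of the Statistical Analysis Plan asks two things about toys. For description, the SAP says of the "preference for toys of children in Attention diversion group and Combination group, frequency distribution percentage will be used". For comparison, it says of children's "choice in toys between Attention diversion group and Combination group, the chi-square test will be used". It does not list the categories, say whether a child contributes one choice or several, or fix the moment at which the choice is recorded. The paragraph then closes with a sentence that also ends the preceding analysis paragraphs: "All the data will be present in a table in the form of median and interquartile range", with mean and standard deviation as the other option.

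The protocol's Interventions section describes what is offered. Distraction-group children choose among several types of distraction: whistles, cartoon books, cartoons on TV and electronic products with games. Of the same children it adds: "They will be also taught breathing exercises", if they are willing. In the combined group the play therapist encourages children to "choose their favorite toys and play that with them 5 minutes before venipuncture or to do breathing exercises as the distraction group". The next sentence reads: "During IV cannulation the play therapist will continue distracting the child with toys".

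**The concern.** A Pearson chi-square test needs each child classified once, by the same rule in both groups. Two features of the text seem to threaten that.

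- **Breathing exercises.** Read literally, a distraction-group child who does them also has a toy to record, whereas a combined-group child may have done them instead of playing with a toy. If the first child is coded by toy and the second as breathing, the test would pick up the coding rule and could report a difference in preference where none exists. A record that showed only breathing could not be turned into a toy afterwards.
- **Unit of count.** Several distractions are on offer and the combined-group text speaks of toys in the plural, so more than one choice per child is possible.

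Medians, means and standard deviations also make no sense for toy type. At stake is the only between-group test planned for toys. The pain, cortisol, heart rate and SpO₂ comparisons do not use it.

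**Working it through.** **Inputs.** The documents give no sample size, category list or expected proportions for this analysis, so there is no stated figure to reproduce. From the documents: four named toy types, two groups, a 5% significance level. Assumed: 20 to 60 children per group, 5% to 30% of children doing breathing exercises, and toy shares equal or 10/20/30/40%, always the same in both groups.

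**Step 1: what one-sided coding does to a table with identical preferences.** Let n be the children per group, m_j the share preferring toy j, and k the combined-group children recorded as breathing instead of a toy. Distraction-group breathing is ignored.

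- Breathing column: 0 and k observed, k/2 expected in each group. Contribution: 2 × (k/2)² / (k/2) = k.
- Toy j: expected m_j(2n − k)/2 in each group, deviation m_j·k/2. Contribution: m_j·k²/(2n − k). Summed over toys: k²/(2n − k).
- Total: X² = k + k²/(2n − k) = 2nk/(2n − k), on 4 degrees of freedom, critical value 9.49.

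| n per group | k | X² | p |
|---|---|---|---|
| 20 | 2 (10%) | 80/38 = 2.11 | 0.72 |
| 20 | 6 (30%) | 240/34 = 7.06 | 0.13 |
| 40 | 4 (10%) | 320/76 = 4.21 | 0.38 |
| 40 | 8 (20%) | 640/72 = 8.89 | 0.064 |
| 40 | 12 (30%) | 960/68 = 14.12 | 0.007 |
| 60 | 6 (10%) | 720/114 = 6.32 | 0.18 |
| 60 | 12 (20%) | 1440/108 = 13.33 | 0.010 |
| 60 | 18 (30%) | 2160/102 = 21.18 | 0.0003 |

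The toy shares drop out of the formula. If only toys are counted, X² = 0 and p = 1.00 in every row. With n = 40 and k = 12, counting every response in both groups gives X² = 0.56, p = 0.97.

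**Step 2: rejection rates with sampling variation** (20,000 simulated trials per cell, identical toy preferences, nominal 5%; ranges run from 30 to 50 per group in the first four rows).

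| Coding rule | Rejection rate |
|---|---|
| Breathing coded in the combined group only, 5% uptake | 6% to 10% |
| Same, 10% uptake | 14% to 32% |
| Same, 20% uptake | 49% to 88% |
| Half of distraction-group users also coded as breathing, 10%; 20% uptake | 6% to 9%; 11% to 16% |
| Breathing coded alike in both groups | 4.5% to 5.0% |
| One toy per child in both groups | 4.6% to 5.3% |
| Children without a toy left out, same preferences as the others | 4.3% to 5.3% |

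**Step 3: does the text lead to one-sided coding?** Three things must happen together: breathing is treated as a toy category, it replaces the toy in the combined group's record, and the same behaviour is disregarded in the distraction group.

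- The SAP question is about toys. The Interventions section mentions breathing exercises apart from toys in both groups, and the word that joins them in "choose their favorite toys and play that with them 5 minutes before venipuncture or to do breathing exercises as the distraction group" marks breathing as something other than a toy.
- That same phrase ends by referring back to the distraction group, which points to the same offer in both.
- "During IV cannulation the play therapist will continue distracting the child with toys" means that a combined-group child who did breathing beforehand still has a toy to record.

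So none of the three conditions follows from the documents.

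**Step 4: unit of count.** With 40 per group and no true difference, 10,000 simulated trials gave 4.9% rejection with one choice per child, 21% when two linked choices per child (the same toy 70% of the time) were treated as independent, and 0.1% when children could tick several toys independently. The first is the ordinary use of the test. The others come from feeding responses, rather than children, into it.

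**Step 5: summary statistics.** The paragraph itself says that "frequency distribution percentage will be used" for toy preference. The later sentence on medians and means repeats stock wording and cannot be applied to toy type, so it leaves no real choice open.

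**The case for a change.** The strongest argument for a change is that the definition really is missing, one sentence would supply it, and the time to do so is before the data are recorded. The wording does differ between groups, and a nurse who followed it literally might enter only breathing for a combined-group child. The unit of count is the better-supported half of the case: plural toys are in the text, and 21% rejection is a real error if linked choices are pooled. Leaving out children without a toy is not always safe either: if breathing users have the reverse toy preferences, rejection runs from 5.6% to 15.4% at 10% to 30% uptake.

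What stands is that the SAP defines neither the choice nor its unit, and that the two descriptions of breathing exercises do not match word for word. What does not stand is the step from there to a biased test. The large figures need a coding that no section states or implies. The unrecoverable record is conjecture, because no case form is in the documents and the text has toys in use during cannulation. Pooling several choices from one child as independent is an analyst's error, not an instruction of the plan. A definition such as the first toy chosen would be one valid option among several, and it need not be the child's favourite.

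**Conclusion.** The concern does not call for a change. Under the ordinary readings of the plan (one toy per child, or breathing coded alike in both groups) the chi-square test rejects in 4.5% to 5.3% of null trials, which is what it should do. The 14% to 88% range belongs to one-sided coding with 10% to 20% breathing uptake and 30 to 50 children per group. All of these are assumptions, and at 20 per group and 10% uptake even the one-sided table gives only p = 0.72.

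What remains is a missing definition that a competent analyst would fill by counting each child once under a common rule, a difference in wording that is probably loose drafting, and a stock sentence on medians that the same paragraph overrides. The question is descriptive, lies outside the stated aim of comparing pain and stress, and feeds into no other analysis. The conclusion rests on children in both groups having a toy recorded by the same rule, as the Interventions section implies. It would need another look only if the records showed breathing in place of a toy in one group alone.
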